[name] and several trainees from the University of California San Francisco (UCSF) and the Mbarara, Uganda, University of Science and Technology (MUST) leveraged the Uganda ARCH cohort into newly funded alcohol/HIV research studies and fellowships. [name] received a prestigious K24 Mid-career Investigator Award in Patient-Oriented Research (NIA K24AA022586) to build her research and mentoring program in HIV/alcohol comorbidity, a UCSF Center for AIDS Research (CFAR) Established Investigator pilot award, and an award from the US Department of Defense. Three junior investigators ([name], [name], and [name]) received UCSF CFAR pilot awards, and [name] received 2 training awards, allowing her to spend 4 months learning research methods and writing in San Francisco.

C. APPROACH

C.1 The proposed study builds on existing collaborative relationships. This research will be conducted in the context of the URBAN ARCH Consortium, leveraging the infrastructure developed over the past five years of the Uganda ARCH cohort as a collaborative effort between UCSF, Boston University (BU), Boston Medical Center (BMC), and MUST. The team includes international experts in alcohol and HIV epidemiology and biomarkers of alcohol use ([name]), clinical research in persons with HIV in Uganda ([name]), TB outcomes in resource limited settings ([name]), decision analytic modeling ([name]), clinical trial design and analysis ([name]), and hair drug concentration ([name]). Consultants include world experts in clinical trials of TB medications ([name]) and HIV/substance use research ([name]).

C.2 Preliminary data for this application

Little evidence of liver damage due to alcohol use. We ([name]) conducted liver enzyme testing in 169 HIV-infected participants in the Uganda ARCH cohort at the baseline visit. A small proportion, 7.6%, had Grade 1/2

Table 2. Baseline characteristics of the Uganda ARCH cohorts (U01 AA020776 and R01 AA018631), n=751.

Male	41%
Age, median (Interquartile range [IQR])	31 (26-39)
CD4 cell count, median (IQR) cells/mm³	462 (330-638)
Log HIV viral load	3.79 (3.00-4.39)
Self-reported alcohol use, prior 3 months	62%
Among current drinkers (prior 3 months, n=465)	
Self-reported heavy drinking: AUDIT-C+	52%
PEth >=50 ng/ml	59%
Heavy drinking (AUDIT-C+ or PEth ≥50 ng/ml)	73%
PEth level, ng/ml, median (IQR)	75.8 (16.0-274.0)

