(5) The eligibility criterion for the proposed study is current (prior 3 month) drinking OR non drinking in the prior year, while the WHO recommendations refer to “regular and heavy alcohol consumption”. We will use “current drinking” because we have found that while half of current drinkers report heavy drinking by the AUDIT-C criteria (52%), a large proportion of current drinkers (21%) have high PEth levels (≥ 50 ng/ml) but do not report heavy drinking (Table 2, above). Thus, an eligibility criterion of current drinking will allow us to examine toxicities among drinkers who do not fully report their level of drinking so that future guidelines can account for under-reporting of drinking.

C.3.3 Study setting and eligibility. This study will be conducted in the Immune Suppression Syndrome (ISS) HIV Clinic of the Mbarara Regional Referral Hospital (MRRH) at MUST, the site of the Uganda ARCH. There are over 12,000 active patients at the ISS Clinic. The ISS Clinic and pharmacy use electronic medical records (EMR) via the Open Medical Record System (OpenMRS). Eligibility criteria will be: ISS clinic patient age ≥ 18 , living within 2 travel hours of the clinic, fluent in Runyankole or English, on ART, and self-reported alcohol consumption in the prior 3 months or abstainer. Exclusion criteria will be as follows: plans to move in the coming 6 months, on nevirapine (NVP, an ART drug that is declining in usage due to high risk for hepatotoxicity), history of active TB, current active TB, prior TB preventive therapy, and ALT or ALT elevation ($>2x$ ULN).

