C.3.4 Enrollment – Eligibility screening and baseline study activities. Participants will initially be recruited from the Uganda ARCH cohorts, in which participants have given permission for re-contact for further study. Of the 465 current drinkers recruited in these cohorts, we estimate that we will be able to contact 75% (N=349), and that 60% of those will meet eligibility criteria (n=209). The remaining participants will be recruited from persons reporting any alcohol use on the AUDIT, approximately 25% of clinic patients,¹⁰⁹ which is routinely administered at initial ISS Clinic visit. We will also recruit patients who report no prior year alcohol use for the abstainer group. We will review the EMR for potential participants and those that meet preliminary study eligibility (i.e. age, on ART for 6 months) will be invited to meet with a research assistant to determine further eligibility. If further eligibility is established, the research assistant, a licensed clinical officer, will seek informed consent for further screening to rule out active TB, existing liver disease, and to assess TST status (Figure 1). A blood draw for ALT/AST testing will be performed, a TST will be placed, and if the participant reports symptoms of possible active TB (cough >24 hours, fever, weight loss, night sweats), further tests (chest X-ray and sputum collection for acid fast bacilli [AFB] stain and Xpert MTB/RIF assay) will be conducted. Those with abnormal chest X-ray results or a positive AFB or Xpert test will be brought to the MRRH TB clinic per hospital protocol. Patients will be asked to return in 2 days for TST reading, informed consent will be requested if active TB has been ruled out and TST is positive. After informed consent is obtained, the baseline visit will include study questionnaire completion, blood draw, and medication dispensing.

Aim 1: To examine the safety and tolerability of 6H for HIV-infected drinkers, measured by hepatotoxicity. Our main aim is to estimate safety overall among drinkers (primary) and by level of drinking (secondary). We will additionally compare safety and tolerability by level of drinking in secondary analyses.

Aim 2: To estimate the level of adherence to TB preventive therapy, overall among drinkers (primary), by month on therapy. Secondarily, we will estimate adherence by drinking level and compare adherence levels across drinking levels. We hypothesize that adherence will be highest among non-drinkers.

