Alcohol consumption. Heavy drinking will be defined as either PEth \geq 50 ng/mL or AUDIT-C positive (\geq 3 for women, \geq 4 for men). The AUDIT-C will be modified to cover the prior 3 months. By combining two highly specific measures, we will increase the sensitivity for detecting heavy alcohol use over using each measure alone, as in our previous analyses of heavy alcohol use by persons with HIV in Uganda.^{81,82}

We will collect self-reported measures of alcohol use at baseline using the AUDIT-C and the CAGE,¹²⁰ which are readily available for use in clinical practice. For analyses that examine level of drinking, we will categorize

the scores as low risk drinking, (women: AUDIT-C 0-2; men: AUDIT-C 0-3), heavy drinking (women: AUDIT-C 3-5; men: AUDIT-C 4-5), and very high risk drinking (AUDIT-C ≥ 8).¹²¹ The corresponding cutoffs for the CAGE will be scores of 0, 1, and 2-4.¹²² We will additionally measure alcohol consumption using tools that are not dependent on standardized drink volume or concentration, e.g. money spent drinking, level of intoxication, and PEth level, as in our previous studies.¹⁰¹

Covariates. Covariates measured at baseline will include gender, age, body mass index (BMI), CD4 cell count, HIV viral load, ALT/AST, active hepatitis B viral infection (HBsAg), symptoms of depression,¹²³ smoking, nicotine dependence,¹²⁴ and duration on ART – also recently added on baseline platelet count, FIB-4 score, and eGFR. Covariates measured at baseline and follow-up will include current ART regimen, and the VAS and SRSI for self-reported ART adherence.

Table 3. Schedule of study visits and activities.

	Eligibility	Baseline	Week 2	Month 1	Month 2	Month 3	Month 4	Month 5	Month 6	Month 7	Follow-up
Initial eligibility determined, ALT/AST and TST testing. Chest X-ray and sputum collected if symptoms of active TB are reported.	X										
Enrollment/ baseline: Study interview, blood draw, medication dispensing		X									
Toxicity assessment (side effects and ALT/AST testing)			X	X	X	X	X	X	X	X	
Medication refill, pharmacy pill count, and EMM data download, and brief alcohol and adherence assessments			X	X	X	X	X	X	X		
Hair collection for INH concentration						X			X		
Follow-up: Study interview, blood draw, and screening for active TB						X			X		X

C.3.9 Statistical analyses for Aim 1.

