Primary analysis: Safety. The focus of this aim is the evaluation of safety among drinkers overall (primary) and by drinking levels (secondary). Thus the primary analysis set will be all participants who receive at least one dose of TB preventive therapy who are current drinkers. We will report the incidence of Grade 3/4 hepatotoxicity at any time during prescribed treatment along with 95% exact binomial confidence intervals (CIs).

Secondary analyses: Safety and tolerability will be estimated by level of alcohol use at baseline and during treatment. To examine safety and tolerability by alcohol consumption prior to treatment, we will report hepatotoxicity and treatment discontinuation stratified by level of drinking (heavy alcohol consumption, current but not heavy drinking, no drinking) at baseline. Fisher's exact test and exact logistic regression models adjusting for gender, hepatitis B co-infection, Cd4 cell count and/or viral suppression will be used to compare safety outcomes across drinking levels. To inform clinical practice, we will also report the outcomes by self-reported alcohol consumption levels using the AUDIT-C and the CAGE. We will also examine toxicity by level of PEth, using recently suggested PEth cutoffs. We will use generalized estimating equation logistic regression models to examine whether drinking level during the treatment period impacts safety and tolerability outcomes.

Secondary analysis: Comparison of hepatotoxicity rates to previous studies. We will also compare estimates and 95% CIs to those reported in published studies of TB preventive therapy in those with HIV, which found hepatotoxicity rates of 0.3-5.5%.

Sample size justification. We anticipate a total of 200 drinkers will be enrolled into the current study. Based on the Uganda ARCH cohort retention, we expect 90% 6-month study visit retention resulting in N=180 evaluable participants. We expect that the proportion of participants with any Grade 3/4 hepatotoxicity within the treatment period will be approximately at the midpoint of the range of toxicity rates published previously, i.e. 2.6%. Given this, we would expect approximately 5 safety events, and the length of a 95% exact binomial CI around the estimate would be 5.5%, (i.e. 0.9% to 6.4%).

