To illustrate power for secondary analyses, we also calculate the minimum detectable difference to compare safety between alcohol groups. I.e., to compare toxicity between any group of drinkers (either heavy drinkers or moderate drinkers, each expected to be approximately 1/3 of the sample) to non-drinkers (1/3 of the sample), we will have 80% power to detect a difference in toxicity rate of 0.095 or greater if the toxicity rate in the lighter drinkers/abstainers is 1% and alpha is set to 0.05 based on a Fisher's Exact test.

C.3.10 Statistical analyses for Aim 2.

Primary analysis: The goal of this aim is to estimate the level of adherence overall among drinkers and by drinking level (including abstainers). The analysis will consist of all participants enrolled. For those who are advised to discontinue therapy by the study physicians, adherence up until discontinuation will be used; however, additional sensitivity analyses will be conducted using alternative imputation strategies (e.g. using the midpoint between best and worst weeks, and assuming the worst case scenario of zero for the discontinued time period). We will report the percent adherence using EMM data over the treatment duration and 95% CIs overall among drinkers and by drinking level (heavy, non-heavy, abstainer), and fit multiple linear regression models, controlling for gender, to compare adherence across drinking categories. If the data are skewed, transformations will be performed (e.g., log transformation) or median regression if no appropriate transformation is identified.

Secondary analyses: Alternate measures of adherence and adherence over time and by level of alcohol use. Secondary measures of adherence will be analyzed using the same approach as described above. We will additionally conduct all adherence analyses excluding the first 40 days to remove a possible Hawthorne effect that may occur when patients are aware they are being monitored, but that often abates after one month. We will also conduct repeated measures analyses of monthly adherence data using linear mixed effects regression models, with month on treatment included as a predictor, to test the hypothesis that adherence changes over time. We will additionally use these analyses to assess whether drinking level at baseline and during treatment (using time-updated covariates) impact adherence.

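### The 80% power stated for any drinker group assumes equal thirds; with the plan's own heavy-drinking definition and 73% heavy share, the non-heavy comparison has about 74% (about 69% after 10% dropout)

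*Combined protocol and SAP*

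**What the plan says.** The secondary power statement in C.3.9 (Sample size justification) reads "we will have 80% power to detect a difference in toxicity rate of 0.095 or greater", with a 1% rate in the reference group, alpha 0.05 and Fisher's exact test. It covers heavy or moderate drinkers against non-drinkers, the two drinker groups being "each expected to be approximately 1/3 of the sample". With 200 drinkers and 100 non-drinkers (Study Design Overview), that means about 100 per group.

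The comparison it illustrates is in the secondary analyses of C.3.9, where outcomes are "stratified by level of drinking (heavy alcohol consumption, current but not heavy drinking, no drinking) at baseline" and compared by Fisher's exact test and exact logistic regression.

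C.3.8 (Alcohol consumption) defines heavy drinking as a composite, PEth at or above 50 ng/mL or a positive AUDIT-C, and gives the reason: "By combining two highly specific measures, we will increase the sensitivity for detecting heavy alcohol use over using each measure alone".

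Table 2 has a row for this composite, "Heavy drinking (AUDIT-C+ or PEth ≥50 ng/ml)", at 73% of the 465 current drinkers. C.3.2, item 5, uses the same data to justify the eligibility rule: 52% report heavy drinking on the AUDIT-C, and "a large proportion of current drinkers (21%) have high PEth levels" without reporting it.

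On the source of participants, C.3.4 says "Participants will initially be recruited from the Uganda ARCH cohorts".

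**The concern.** The composite was chosen to classify more drinkers as heavy, and in the source cohorts it classifies nearly three quarters of them that way. The power statement nevertheless assumes an even split. If the trial's drinkers resemble the source cohorts, the non-heavy group is about half the assumed size and its comparison with non-drinkers falls short of 80%, while the heavy comparison exceeds it. One figure cannot describe both.

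What is at stake is interpretation. A null result for non-heavy drinkers against non-drinkers would be read as coming from a comparison with 80% power for a 9.5-point difference, which the plan's own figures do not support.

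**Working it through.** **Inputs**

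- 200 drinkers and 100 non-drinkers: Study Design Overview.
- 1% versus 1% + 9.5% = 10.5%, alpha 0.05, Fisher's exact test: C.3.9. The plan does not say whether the test is one- or two-sided; two-sided is assumed.
- Heavy share 73% under the composite: Table 2. Cross-check from C.3.2: 52% + 21% = 73%.
- Retention 90%: C.3.9, "we expect 90% 6-month study visit retention resulting in N=180 evaluable participants". The plan states this for drinkers; applying it to non-drinkers is an assumption here.

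**Method**

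Power = Σₓ Σᵧ Bin(x; n₁, 0.01) · Bin(y; n₂, 0.105) · 1[two-sided Fisher p ≤ 0.05], summed over all possible tables.

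**Step 1: reproduce the plan's figure**

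100 versus 100 gives 80.7%, and the difference detectable with 80% power is 0.094. The one-sided test would give 87.6%. The stated figure therefore rests on a two-sided test, 100 per group and no dropout.

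**Step 2: group sizes under the composite**

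- Heavy: 200 × 0.73 = 146 (49% of 300).
- Non-heavy: 200 × 0.27 = 54 (18% of 300).
- Non-drinkers: 100 (33% of 300).
- With 90% retention: about 131 heavy and 49 non-heavy of 180, and 90 non-drinkers.

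**Step 3: power at a 73% heavy share**

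Exact Fisher power is saw-toothed in the group sizes: 53 versus 100 gives 79.1%, and 54 versus 100 gives 71.1%. A single pair of sizes can mislead, so the averages weight power by a binomial split, Bin(200, share) against 100 or Bin(180, share) against 90.

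| Comparison with non-drinkers | At the expected sizes | Average power | Average detectable difference |
|---|---|---|---|
| Non-heavy, no dropout | 54 v 100: 71.1% | 73.9% | 0.106 |
| Non-heavy, 90% retention | 49 v 90: 66.5% | 68.8% | 0.115 |
| Heavy, no dropout | 146 v 100: 91.4% | 90.8% | 0.078 |
| Heavy, 90% retention | 131 v 90: 87.1% | 86.7% | 0.085 |

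For the non-heavy comparison, the range over nearby sizes is 71–79% (n = 50–58 versus 100) without dropout and 67–75% (n = 45–53 versus 90) with it. If retention is applied to drinkers only (180 drinkers, 100 non-drinkers), the non-heavy average is 71.7%.

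**Step 4: dependence on the heavy share (average power, non-heavy versus non-drinkers)**

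| Heavy share | No dropout | 90% retention |
|---|---|---|
| 50% | 84.2% | 79.0% |
| 60% | 82.0% | 77.1% |
| 65% | 78.5% | 73.3% |
| 70% | 75.1% | 70.0% |
| 73% | 73.9% | 68.8% |
| 80% | 64.2% | 58.5% |

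Without dropout the average crosses 80% at a heavy share of about 63% (62%: 80.8%; 63%: 80.0%; 64%: 79.3%). Compared on the same averaged basis, moving from 50% to 73% costs 84.2 − 73.9 = 10.3 points. The gap is therefore not a saw-tooth artefact.

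**Step 5: single-measure definitions, no dropout**

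- AUDIT-C alone (52% heavy): 104 versus 100 gives 83.4%; 96 versus 100 gives 85.3%.
- PEth alone (59% heavy): 118 versus 100 gives 89.1%; 82 versus 100 gives 83.3%.

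Both keep 80%, so the shortfall is specific to the composite.

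**The case against.** The strongest objection is that 73% is not a forecast for this trial. It was measured at baseline in earlier cohorts, and this trial enrols people on ART. C.2 reports that heavy drinking, by the same composite, fell before ART start and rose after it. The 209 eligible drinkers projected in C.3.4 (465 × 0.75 = 349; 349 × 0.60 = 209) allow nothing for refusal, and the plan expects to top up from the clinic, for which it gives no heavy share. This stands: the true share is unknown, and the shortfall without dropout appears only above about 63%. But 73% is the only composite figure in the documents, it comes from the first recruitment source, and nothing in the plan supports 50% under the composite.

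Second, the plan's arithmetic is right on its own inputs. That is so. The fault is an input that conflicts with Table 2, not a miscalculation.

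Third, the retention scenario is open to challenge, because the safety set is everyone who takes at least one dose and toxicity is assessed from week 2. That is fair, and the no-dropout figure should carry the argument. Retention matters less than the split. At equal thirds it lowers the average from 84.2% to 79.0%; exactly 90 versus 90 gives 74.2%, but that is a trough.

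Fourth, the effect is small. The average detectable difference is 0.106 against the stated 0.095, and the heavy comparison, which is closest to the WHO exclusion, is better powered than stated. Both facts are correct and limit the importance of the point.

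**Conclusion.** The concern holds, as a minor one. The 80% claimed for either drinker group requires about 100 in each. Under the plan's composite definition and its source cohorts' 73% heavy share, the non-heavy comparison averages 73.9% without dropout and 68.8% with 90% retention in both groups. The heavy comparison averages 90.8% and 86.7%. The single figure is thus too high for one planned comparison and too low for the other.

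This rests on a two-sided test, the stated 1% and 10.5% rates, and the source-cohort share carrying over, which is uncertain. The statement is illustrative and secondary: the enrolment target and the primary precision calculation are untouched, and no decision rule depends on it.

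**What to change.** In C.3.9, replace the one-third assumption and the single figure with power, or detectable difference, given separately for heavy versus non-drinkers and non-heavy versus non-drinkers. Use the composite definition and a range of heavy shares that includes 73%, for example 50%, 60%, 73% and 80%. Show results with and without 90% retention, because the safety set is everyone dosed. State whether the test is one- or two-sided. Note that exact Fisher power is saw-toothed, and report either averages over the random split or ranges.

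The cost is one rewritten paragraph or a small table. Enrolment and the primary analysis do not change. The only drawback is a less favourable figure for the non-heavy comparison.

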We propose a single arm trial of TB preventive therapy to assess its toxicity, measure adherence, and determine whether its benefits outweigh its risks when given to TB/HIV-infected drinkers (n=200). We will provide 6 months of INH to HIV/TB infected drinkers (n=200) and non-drinkers (n=100) to describe safety, tolerability, and adherence among drinkers and by level of drinking. We will conduct frequent monitoring for toxicity, and assess toxicity as well as adherence. We will evaluate the safety, tolerability and adherence by level of drinking, measured by self-report and augmented by phosphatidylethanol (PEth), an established biomarker for alcohol consumption. We will employ objective measures of adherence, including electronic medication monitoring (EMM) of pill bottle opening, pharmacy pill counts, and a novel measure of INH exposure, that is, INH concentration in hair. We will actively monitor for toxicity, using the U.S. standard of care for laboratory monitoring during TB preventive therapy for heavy drinkers. We will use the safety, tolerability, and adherence results, together with the known efficacy and mortality benefit of TB preventive therapy in HIV-infected persons in SSA, and our established decision analytic model of TB preventive therapy, to determine whether the mortality and quality of life benefits of TB preventive therapy outweigh the toxicity risks for HIV-infected drinkers in resource limited settings.

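### Fisher's exact test is valid but very conservative for the secondary drinking-level toxicity comparisons; a stated variant of Boschloo's exact test keeps the 5% level and never has less power

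*Combined protocol and SAP*

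**What the plan says.** C.3.9 (Secondary analyses) compares safety outcomes across three baseline drinking levels: heavy, current but not heavy, and none. It uses Fisher's exact test together with "exact logistic regression models adjusting for gender, hepatitis B co-infection" and markers of HIV disease.

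C.3.9 (Sample size justification) illustrates power for one drinker group against non-drinkers: "we will have 80% power to detect a difference in toxicity rate of 0.095 or greater", with a 1% rate in the lighter-drinking or abstaining group and "alpha is set to 0.05 based on a Fisher's Exact test". The drinker group is "either heavy drinkers or moderate drinkers, each expected to be approximately 1/3 of the sample", and non-drinkers are the remaining third. The Study Design Overview gives 200 drinkers and 100 non-drinkers.

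The same section expects a Grade 3/4 rate of 2.6% among drinkers and states "we expect 90% 6-month study visit retention resulting in N=180 evaluable participants". The primary analysis is the incidence among drinkers with an exact binomial interval, so the Fisher comparisons are secondary. No unconditional exact test is mentioned.

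**The concern.** Fisher's test conditions on the total number of events. The design does not fix that total, and when events are rare the conditional distribution has so few attainable p-values that the true type I error falls far below 5%. Power is lost with it. An unconditional exact test can recover part of that loss and still control the error rate exactly.

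Safety is the study's primary outcome (C.3.2), and C.4.4 asks whether the approach to preventive therapy should differ by level of drinking. A test that uses less of its permitted error rate than it could is therefore a poor default for these comparisons, even though they are secondary.

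**Working it through.** **Inputs.** From C.3.9: alpha 0.05, Fisher's exact test, reference rate 1%, difference 0.095 (so 10.5% v 1%), groups of about one third, expected rate 2.6%, retention 90%. From the Study Design Overview: 300 participants, so 100 v 100. From Table 2: 73% of current drinkers are heavy, giving 0.73 × 200 = 146 heavy and 200 − 146 = 54 not heavy. The plan does not state sidedness; two-sided is assumed.

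**Formulas.** For x events of n1 and y of n2, let pF(x,y) be the two-sided Fisher p-value: the sum of hypergeometric probabilities, given x + y, that do not exceed that of the observed table.

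- Power = Σx Σy Bin(x; n1, p1) · Bin(y; n2, p2) · 1{pF(x,y) ≤ c}, with c = 0.05 for Fisher.
- Size at a common rate p is the same sum with p1 = p2 = p.
- Boschloo (this variant) uses the largest c for which the maximum size over all p is at most 0.05. Fisher's own maximum size is below 0.05, so c is at least 0.05 and the rejection region contains Fisher's.

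**Step 1: the plan's figure.** At 100 v 100 and 10.5% v 1%, two-sided Fisher power is 80.7%, and the difference giving 80% power is 0.0945. The stated 0.095 reproduces. One-sided Fisher gives 87.6%, so the two-sided reading fits.

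**Step 2: true size.**

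| Common rate | Fisher, 100 v 100 | Boschloo, 100 v 100 |
|---|---|---|
| 1% | 0.04% | 0.25% |
| 2% | 0.46% | 1.4% |
| 2.6% | 0.9% | 2.0% |
| 3% | 1.13% | 2.2% |
| Maximum over all rates | 4.0% | 4.96% |

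At 90 v 90 the maxima are 3.7% and 4.99%. Boschloo is also conservative at low rates, but less so.

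**Step 3: power at 10.5% v 1%.**

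| Groups | Fisher | Boschloo | Gain (points) | Detectable difference at 80% power, Fisher v Boschloo |
|---|---|---|---|---|
| 100 v 100 | 80.7% | 83.9% | 3.2 | 0.0945 v 0.0895 |
| 90 v 90 | 74.2% | 82.3% | 8.1 | 0.103 v 0.0915 |
| 54 v 100 | 71.1% | 80.1% | 9.0 | 0.1105 v 0.095 |
| 146 v 100 | 91.4% | 92.3% | 0.9 | 0.0775 v 0.0745 |
| 100 v 95 | – | – | 0.0 | – |
| 110 v 110 | – | – | 0.0 | – |

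The gain is erratic because it depends on which few tables are added to the rejection region. With no events in non-drinkers, Fisher needs 6 in the drinker group and Boschloo 5, both at 100 v 100 and at 90 v 90. With one event in non-drinkers, both need 8 at 100 v 100; at 90 v 90 Fisher needs 8 and Boschloo 7.

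**Step 4: smaller differences.** At 5.5% v 1%, 100 v 100, power is 25.2% with Fisher and 32.6% with Boschloo. At 2.6% v 1% it is 1.9% and 4.6%.

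**Step 5: the variant matters.** Some software doubles a one-sided Boschloo p-value; scipy's routine does. At 54 v 100 with 3 v 0 events, Fisher gives p = 0.042 and that routine gives p = 0.059. Over all tables at 10.5% v 1%, the doubling version has 67.4% power against Fisher's 71.1%.

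**The case against.** The strongest reply is that nothing here is wrong. Fisher's test is valid, its stated figure reproduces, the comparison is secondary and offered as an illustration, and the adjusted exact logistic regression is untouched by the change. All of that stands, and it limits the point to an efficiency suggestion.

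Three stronger readings are tempting, and the documents do not support them.

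- A reader might infer a gain of several points whatever the layout. It is 0.9 points for heavy v none under the Table 2 split, arguably the comparison closest to the WHO exclusion, and 0.0 at 100 v 95.
- A reader might infer that the plan's power should have been computed at 90 per group, where Fisher has 74.2%. The 90% retention is stated for drinkers only. The primary safety set is current drinkers with at least one dose, and toxicity is assessed at week 2 and then monthly, so a late drop-out still contributes safety data. The 90 v 90 case is an assumption.
- A reader might infer that Fisher is the reason a real excess would be missed. C.3.9 expects about 5 events among drinkers (0.026 × 180 = 4.7). At 2.6% v 1% the excess is missed about 95% of the time or more with either test. The larger gains apply to a roughly tenfold difference, above the 0.3-5.5% range that C.3.9 cites.

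It is also fair to say that C.3.9 compares outcomes across three levels, whereas Boschloo's test as used here is for a 2×2 table. It can serve only the pairwise comparisons, which is the form of the plan's own power statement. It does not settle multiplicity between them.

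**Conclusion.** The point holds as a minor improvement to a secondary analysis. At event rates of 1-3%, Fisher's true size at 100 v 100 is roughly 0.04% to 1.1%. Boschloo's test built on the two-sided Fisher p-value keeps the 5% level and cannot have less power. In the layouts examined at 10.5% v 1%, the gain runs from 0 to about 9 points.

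This rests on two-sided 5% testing and independent binomial groups. The 100 v 100 figures also need equal thirds, the 54 and 146 figures need the Table 2 heavy share to carry over to this trial, and the 90 v 90 figures need non-drinkers to be retained at 90% as well. The benefit depends on the variant: naming Boschloo's test without specifying it could cost power where the groups are unequal.

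**What to change.** In C.3.9, for the two unadjusted pairwise comparisons (heavy v none, current-not-heavy v none), specify Boschloo's unconditional exact test at two-sided 5% with the two-sided Fisher p-value as the test statistic, and exclude the version that doubles a one-sided p-value. Name the software and confirm which version it computes.

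State the detectable difference with the group sizes assumed: about 0.0895 at 100 v 100, or 0.0915 at 90 v 90 if 10% loss is assumed in both groups.

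Keep exact logistic regression for the adjusted analysis, and a Fisher-type exact test for any overall three-level comparison.

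The cost is a sentence or two in the plan and, if the available routine uses doubling, a short enumeration program. No further participants or data are needed.
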